7.4 Statistical Analyses for Safety

Safety will be assessed by AEs, physical examination, laboratory assessments, and vital signs. Note that missing safety data will not be imputed. Analysis details will be specified in the SAP.

Adverse events will be coded using the Medical Dictionary for Regulatory Activities (MedDRA). Treatment-emergent adverse events are defined as those that began or worsened in severity after the first dose of study drug and no more than 30 days after the last dose of the study drug. The number and percentage of subjects experiencing TEAEs will be tabulated using the MedDRA SOC and PT, by severity, and by relationship to the study drug as assessed by the investigator. Summaries (including percentages and events per 100 patient-years) of SAEs, deaths, AEs leading to discontinuation, and AESI will be provided as well.

For laboratory and vital signs, mean change from Study M16-046 Baseline and percentage of subject with evaluations meeting criteria for pre-defined Potentially Clinically Significant values will be summarized.

7.5 Statistical Analysis of Optional Proteomic Biomarker Data

Analysis may be conducted on optional biomarker data for the purpose of identification of prognostic, predictive, surrogate, and pharmacodynamic biomarkers associated with efficacy or safety. The

association of biomarkers to the efficacy or safety endpoints may be explored for each biomarker one at a time, and also for combinations of biomarkers via some multivariate predictive modeling approaches.

8 ETHICS

8.1 Independent Ethics Committee/Institutional Review Board

The protocol, informed consent form(s), recruitment materials, and all subject materials will be submitted to the Independent Ethics Committee/Institutional Review Board (IEC/IRB) for review and approval. Approval of both the protocol and the informed consent form(s) must be obtained before any subject is enrolled. Any amendment to the protocol will require review and approval by the IEC/IRB before the changes are implemented to the study. In addition, all changes to the consent form(s) will be IEC/IRB approved.

8.2 Ethical Conduct of the Study

The study will be conducted in accordance with the protocol, Operations Manual, International Council for Harmonisation (ICH) guidelines, applicable regulations, and guidelines governing clinical study conduct and the ethical principles that have their origin in the Declaration of Helsinki. Responsibilities of the investigator are specified in Appendix B.

In cases of state of emergency or pandemic situations leading to difficulties in performing protocol-specified procedures, AbbVie will engage with study site personnel in efforts to ensure the safety of subjects, maintain protocol compliance, and minimize risks to the integrity of the study while trying to best manage subject continuity of care. This may include alternative methods for assessments (e.g., phone contacts or virtual site visits), alternative locations for data collection (e.g., use of a local lab instead of a central lab), and shipping investigational product and/or supplies direct to subjects to ensure continuity of treatment where allowed. Refer to the Operations Manual for additional details. In all cases, these alternative measures must be allowed by local regulations and permitted by IRB/IEC. Investigators should notify AbbVie if any urgent safety measures are taken to protect the subjects against any immediate hazard.

8.3 Subject Confidentiality

To protect subjects' confidentiality, all subjects and their associated samples will be assigned numerical study identifiers or "codes." No identifiable information will be provided to AbbVie.

In cases of state of emergency or pandemic situations, remote monitoring of data may be employed if allowed by the local regulatory authority, IRB/IEC, and the study site.

9 SOURCE DOCUMENTS AND CASE REPORT FORM COMPLETION

The investigator is responsible for ensuring the accuracy, completeness, legibility, and timeliness of the data reported. All source documents should be attributable, legible, contemporaneous, original,

accurate, and complete to ensure accurate interpretation of data. Clinical site monitoring is conducted to ensure that the rights and well-being of human subjects are protected, that the reported trial data are accurate, complete, and verifiable, and that the conduct of the trial is in compliance with the currently approved protocol, ICH Good Clinical Practice (GCP), and applicable local regulatory requirement(s). During the COVID-19 pandemic, remote monitoring of data may be employed if allowed by the local regulatory authority, IRB/IEC, and the study site.

Electronic Patient Reported Data

Patient reported data must be completed for each subject enrolled in this study. Some of these data are being collected with an Electronic Patient Reported Outcome (ePRO) system called Trialmax, provided by the technology vendor CRF Health of Plymouth Meeting, PA, USA. The ePRO system is in compliance with Title 21 CFR Part 11. The documentation related to the system validation of the ePRO system is available through the vendor, CRF Health, while the user acceptance testing of the study-specific PRO design will be conducted and maintained at AbbVie.

The subject will be entering the data on an electronic device; these data will be uploaded to a server. The data on the server will be considered source, and maintained and managed by CRF Health. Worst Pruritus NRS will be completed electronically via an onsite tablet device. The ePRO data of HN-PGIS will be collected electronically via an onsite tablet device into which the subject will directly enter the required pieces of information at visits specified in the Operations Manual Section 2.1 (Individual Treatment Period Visit Activities). The electronic tablet device will be programmed to allow data entry for only the visits specified in the protocol and will not allow for subjects to complete more than one of the same assessments at any one visit. All data entered on the devices will be immediately stored to the devices itself and automatically uploaded to a central server administrated by CRF Health. The investigator and delegated staff will be able to access all uploaded subject entered data via a password protected website, up until the generation, receipt and confirmation of the study archive.

Internet access to the ePRO data will be provided by CRF Health for the duration of the study. This access will be available for the duration of the study to the site investigator, as well as delegated personnel. Such access will be removed from investigator sites following the receipt of the study archive. Data from the ePRO system will be archived on appropriate data media (CD-ROM, etc.) and provided to the investigator at that time as a durable record of the site's ePRO data. It will be possible for the investigator to make paper print-outs from that media.

10 DATA QUALITY ASSURANCE

AbbVie will ensure that the clinical trial is conducted with a quality management system that will define quality tolerance limits in order to ensure human subject protection and reliability of study results. Data will be generated, documented, and reported in compliance with the protocol, ICH GCP, and applicable regulatory requirements.

11 COMPLETION OF THE STUDY

The end-of-study is defined as the date of the last subject's last visit.

APPENDIX A. STUDY SPECIFIC ABBREVIATIONS AND TERMS

Abbreviation Definition

AD atopic dermatitis

AE adverse event

AESI adverse events of special interest

BCG bacilli Calmette-Guérin

BSA body surface area

CAC Cardiovascular Adjudication Committee

CI confidence interval

CLDN1 Claudin 1

CNS central nervous system

COVID-19 Coronavirus Disease – 2019

CPK creatine phosphokinase

CRF case report form

CTCAE Common Terminology Criteria for Adverse Events

CYP3A cytochrome P450 3A isoform subfamily

DNA deoxyribonucleic acid

DTP Direct-to-patient

EASI Eczema Area and Severity Index

ECG Electrocardiogram

eCRF electronic case report form

EDC electronic data capture

ePRO Electronic Patient Reported Outcome

EU European Union

EudraCT European Clinical Trials Database

FLG Filaggrin

FSH follicle-stimulating hormone

GCP Good clinical practice

GI gastrointestinal

HLA Human Leukocyte Antigen

HN-PGIS Head and Neck - Patient Global Impression of Severity

hs-CRP High-sensitivity C reactive protein

ICH International Council for Harmonisation

IEC Independent ethics committee

IEC/IRB Independent Ethics Committee/Institutional Review Board

IGA Investigator's Global Assessment

IgE Immunoglobulin E

IGRA Interferon Gamma Release Assay

IL interleukin

IMP Investigational Medicinal Product

IRB Institutional review board

IRT Interactive response technology

ITT intent-to-treat

IU International Unit

IUD intrauterine device

IUS Intrauterine hormone-releasing system

JAK1 Janus kinase 1
JAK2 Janus kinase 2

MACE major adverse cardiac event

MedDRA Medical Dictionary for Regulatory Activities

NCI National Cancer Institute

NK natural killer

NMSC non-melanoma skin cancer

NRS numerical rating scale

OC Observed Cases

OLE open-label extension

PD visit Premature Discontinuation visit

PK Pharmacokinetic(s)

PPD purified protein derivative (tuberculin)

PRO patient-reported outcome

Ps psoriasis

PT preferred term

PUVA psoralen and ultraviolet A radiation

QD once a day

QTc QT interval corrected for heart rate

QTcF QT interval corrected for heart rate using Fridericia's formula

RA rheumatoid arthritis

RNA ribonucleic acid

RSI Reference Safety Information

SAE Serious adverse event

SAP Statistical analysis plan

SARS-CoV-2 Severe acute respiratory syndrome coronavirus 2

SOC system organ class

SUSAR Suspected unexpected serious adverse reactions

TA MD Therapeutic Area Medical Director

TB tuberculosis

TEAE treatment-emergent adverse event

TNF tumor necrosis factor

Tyk2 tyrosine kinase 2
US United States

UV ultraviolet

WBC white blood cell

APPENDIX D. ACTIVITY SCHEDULE

The individual activities are described in detail in the Operations Manual (Appendix F). Allowed modifications due to COVID-19 are detailed within the Operations Manual.

Study Activities Table

Activity The activities performed at the Week 24 visit of Study M16-046 will be considered the Baseline activity for Study M19-850 (activities with blue checkmarks in Baseline column only).	Baseline	Week 4	Week 8	Week 16	Week 28	Week 40	Week 52	Unscheduled Visit	PD Visit	30 Days After Last Dose
Visit Window (days)	Ba	±3	±3	±3	± 7	± 7	± 7	Ď	P	±3
□ INTERVIEWS & QUESTION	NAIRI	ES								
Informed consent	*									
Eligibility criteria	✓									
Adverse event assessment	✓	✓	✓	✓	✓	✓	✓	✓	✓	*
Prior/concomitant therapy	✓	✓	✓	✓	✓	✓	✓	✓	✓	✓
Latent TB risk factor questionnaire (annually after last assessment in Study M16-046)					*					
Review pregnancy avoidance recommendations (females of childbearing potential only)	~	>	>	*	*	>	*	*	>	
PROS										
Worst Pruritus NRS	✓	✓	✓	✓	✓	✓	✓	V	✓	
HN-PGIS	✓	✓		✓						
TLOCAL LABS & EXAMS										
Body Weight	✓	✓		✓		✓				
Vital Signs (at FU if needed to monitor AEs)	~	*		✓		✓				*
Physical Exam (at follow-up if needed to monitor AEs)	~									*
Investigator Assessment (EASI, BSA)	✓	✓	✓	✓	✓	✓	✓	✓	✓	
Chest x-ray (annually after last assessment in Study M16-046 if newly positive TB results)					*					
12-Lead ECG					✓					

Activity The activities performed at the Week 24 visit of Study M16-046 will be considered the Baseline activity for Study M19-850 (activities with blue checkmarks in Baseline column only).	Baseline	Week 4	Week 8	Week 16	Week 28	Week 40	Week 52	Unscheduled Visit	PD Visit	30 Days After Last Dose
Visit Window (days)	Bas	±3	±3	±3	± 7	± 7	± 7	Uns	PD	±3
Urine pregnancy test for all female subjects of childbearing age. Monthly home urine pregnancy testing will be performed for visits with > 1 month interval. In case of a positive urine pregnancy test a serum pregnancy test will be performed.	~	~	*	*	*	*	*	*	*	1
TENTRAL LABS										
Clinical chemistry, hematology, urinalysis	✓	~	*	*	*	*	1	*	V	√(only as needed for AEs)
hsCRP	✓	✓	✓				✓	V	✓	
QuantiFERON-TB Gold test (and/or local PPD skin test)					*					
Total serum Immunoglobulin E (IgE)	✓	✓		✓			✓			
Optional Biomarker Sample: Skin biopsy (lesional/non-lesional)	~			*						
Optional Biomarker Sample: Whole blood (DNA/RNA/Serum/Plasma)	~	*		~			1			
R TREATMENT										
Dispense study drug (excluding Week 52)	✓		✓ _	✓ _	✓ _	✓				

APPENDIX E. PROTOCOL SUMMARY OF CHANGES

Previous Protocol Versions

Protocol	Date
Version 1.0	28 May 2019
Version 1.1 (VHP countries only)	26 July 2019
Version 2.0	26 August 2019
Version 3.0	28 January 2020
Version 3.1 (Germany and Czech Republic only)	02 April 2020
Version 4.0	06 March 2020
Version 4.1 (Germany and Czech Republic only)	10 June 2020
Version 4.1.1 (Germany only)	31 July 2020

The purpose of this Amendment is to incorporate the following changes:

Summary of Protocol Changes:

The purpose of this version is to incorporate necessary protocol modifications due to the COVID-19 pandemic, add an interim analysis, incorporate additional description about management of gastrointestinal performation and serious herpes zoster, and provide clarification about the timing of efficacy assessments.

Protocol modifications due to the COVID-19 pandemic are as follows:

- Section 2.2 included information on the re-evaluation of the benefit and risk to subjects participating in the study. There is no additional risk to subjects or state what the additional risks are that may change the benefit-risk balance to participating subjects.
- Section 5.5 added instructions to refer to Operations Manual for necessary changes to activities or procedures in the event of temporary study [drug] interruption/halt.
- Section 5.7 included instructions that in the event the subject cannot pick up study drug onsite, refer to the Operations Manual for DTP shipment as needed and permitted by local regulations.
- Section 5.9 clarified that protocol deviations may include modifications due to COVID-19.
- Section 8.2 noted that AbbVie will modify the study protocol as necessary due to the pandemic, referring to the Operations Manual in Appendix F for additional details. Investigators must also notify AbbVie if any urgent safety measures are taken.
- Section 9 noted that remote monitoring may be employed as needed
- Appendix D added reference to Operations Manual for allowed modification

Appendix F – Operations Manual updated to include details on how to perform specific
activities/procedures that may be impacted by changes in global/local regulations due to the
pandemic.

Statements about the interim analysis were added to the following subsections to incorporate this change:

- Section 4.1 Sentence added that an interim analysis will be performed after all subjects have completed the Week 16 visit.
- Section 7.1 Sentence added that an interim analysis will be performed after all subjects have completed the Week 16 visit and all data pertaining to Week 16 are cleaned.

Rationale: To assess efficacy and safety after switching from dupilumab to upadacitinib at a similar timeframe as the upadacitinib atopic dermatitis pivotal Phase 3 studies.

Updates to the description and management of gastrointestinal perforation (added text underlined) were made to:

- Section 5.5 "Subject develops a gastrointestinal perforation (defined as acute, spontaneous perforation of the gastrointestinal tract that requires inpatient medical care or urgent surgical intervention other than appendicitis or mechanical injury). See also Section 6.2 Toxicity Management."
- Section 6.2 Management of Serious Gastrointestinal Events Subjects presenting with the
 onset of signs or symptoms of a gastrointestinal perforation should be evaluated promptly for
 early diagnosis and treatment. Subjects with acute, spontaneous perforation of the
 gastrointestinal tract that requires inpatient medical care or urgent surgical intervention (except
 for appendicitis or mechanical injury) must be permanently discontinued from study drug.

Rationale: To provide further clarity on the characteristics of GI perforations for investigators and requirement for permanent discontinuation of study drug.

Other changes:

 Synopsis and Section 3.3 – Wording was updated to state that efficacy endpoints will be assessed at all visits through Week 52 only.

Rationale: To provide clarification about the timing of efficacy assessments.

• Section 6.2 – Wording about management of herpes zoster was added: "Serious AEs of herpes zoster should be reported as serious infections."

Rationale: To incorporate wording from protocol version 4.1.1.

Section 6.2 – Management of Hypersensitivity was removed. Management of hypersensitivity
was included in Study M16-046 for subjects who received dupilumab and is not used in studies
in which upadacitinib is the only treatment drug. No subjects receive dupulimab in this
extension study.

Rationale: Management of hypersensitivity is not needed in studies when upadacitinib is the only treatment drug.

1.0 Introduction

This Statistical Analysis Plan (SAP) describes the statistical analyses for upadacitinib Study Protocol M19-850, A Phase 3b, open-label treatment extension study of upadacitinib for the treatment of adult subjects with moderate to severe atopic dermatitis who completed treatment in Study M16-046.

Study M19-850 examines the long-term safety, tolerability and efficacy of upadacitinib in adult subjects with moderate to severe atopic dermatitis who successfully completed treatment in Study M16-046.

The SAP will not be updated in case of administrative changes or amendments to the protocol unless the changes impact the analysis.

Unless noted otherwise, all analyses will be performed using SAS Version 9.4 (SAS Institute Inc., Cary, NC 27513) or later under the UNIX operating system.

This SAP includes changes to analyses described in the protocol. Details are outlined in Section 14.0.

[figure not shown]
2.0 Study Design and Objectives

2.1 Objectives, Hypotheses and Estimands

The objective of this study is to assess the long-term safety, tolerability and efficacy of upadacitinib in adult subjects with moderate to severe AD who successfully completed treatment in Study M16-046.

2.2 Study Design Overview

This is a Phase 3b, single arm, open-label extension (OLE) study for adults (18 – 75 years of age at entry into Study M16-046) with moderate to severe AD who have successfully completed treatment in Study M16-046. These subjects should be determined to be eligible to continue treatment with upadacitinib by the Principal Investigator during the

Baseline visit of this OLE study. The Baseline visit for this study will be the Week 24 visit of Study M16-046.

The study is comprised of a Baseline visit (Week 24 visit of Study M16-046), a 52-week open-label treatment period, and an 84-Week End-of-Study Follow-Up Visit (or phone call if a visit is not possible 30 days after the last dose of upadacitinib). End-of-Study Follow-Up visits are only applicable for the following countries and regions: Germany, France, Finland, Netherlands, Norway, Taiwan, Croatia, Poland, Czech Republic, and Hungary. The 30-day follow-up visit is done to determine the status of any ongoing AEs/SAEs or the occurrence of any new AEs/SAEs is required. These subjects will be considered as having completed the study. Subjects, who are eligible to enroll in the OLE study, will receive daily oral doses of upadacitinib 30 mg from the Baseline visit up to the Week 52 visit. The schematic of the study is shown in Figure 1.

[figure not shown]
Safety and efficacy assessments will be performed through Week 52 for all sites, and additional safety assessments will be performed every 12 weeks after Week 52 up to Week 136 for sites in the following countries and regions: Germany, France, Finland, Netherlands, Norway, Taiwan, Croatia, Poland, Czech Republic, and Hungary.

See Section 5.0 of the protocol for information regarding eligibility criteria.

An interim analysis will occur after all ongoing subjects have completed the Week 16 visit. The schematic of the study is shown in Figure 1.

The Final database lock will take place after all subjects complete the study.

Figure 1. Study Schematic

QD=once daily

a. Efficacy evaluations will not be performed after Week 52.

2.3 Treatment Assignment and Blinding

All subject enrolled to M19-850 will receive open label upadacitinib 30 mg QD throughout the study.

The type and amount of kits dispensed will be managed by the Interactive Response Technology (IRT).

2.4 Sample Size Determination

Approximately 600 subjects who complete treatment in Study M16-046 will roll over in this open label treatment extension study. The sample size is determined by the expected rate of completion of Study M16-046 and subject consent for the extension.

3.0 Endpoints

3.1 Primary Endpoints

There is no primary efficacy endpoint for this study.

The primary safety endpoints are:

- Treatment emergent adverse events (TEAEs);
- Serious adverse events (SAEs);
- Adverse events of special interest (AESI);
- AEs leading to discontinuation of study drug;
- Vital signs, laboratory tests, and physical examination findings

[figure not shown]
3.2 Secondary Endpoints

There is no secondary efficacy endpoint for this study.

3.3 Other Efficacy Endpoints

The following efficacy endpoints will be assessed at all visits through Week 52. Baseline refers to the Baseline value in Study M16-046. All endpoints are defined relative to the Baseline values in Study M16-046.

- Change and percent Change from Baseline in EASI;
- Change and percent change from Baseline in Worst Pruritus Numerical Rating Scale (NRS);
- Proportion of subjects achieving EASI 75/90/100;
- Change from Baseline in body surface area (BSA);
- Proportion of subjects achieving an improvement (reduction) in Worst Pruritus NRS ≥ 4 from Baseline among subjects who had Worst Pruritus NRS ≥ 4 at Baseline;
- Proportion of subjects achieving 75% reduction in EASI in the head and neck body region from Baseline;

- Proportion of subjects achieving 75% reduction in EASI in each body region (other than head and neck) from Baseline;
- Proportion of subjects achieving 75% reduction in EASI in the head and neck body region among subjects who received dupilumab in Study M16-046 and did not achieve 75% reduction in EASI in the head and neck body region at Week 24 of Study M16-046;
- Proportion of subjects achieving 75%/90%/100% reduction in EASI (EASI 75/90/100) among subjects who received dupilumab in Study M16-046 and did not achieve EASI 75 at Week 24 of Study M16-046;
- Proportion of subjects achieving EASI 90/100 among subjects who received dupilumab in Study M16-046 and did not achieve EASI 90 at Week 24 of Study M16-046;
- Proportion of subjects achieving EASI 100 among subjects who received dupilumab in Study M16-046 and did not achieve EASI 100 at Week 24 of Study M16-046;
- Proportion of subjects achieving an improvement (reduction) in Worst Pruritus NRS reduction ≥ 4 among subjects who had Worst Pruritus NRS ≥ 4 at Baseline, received dupilumab in Study M16-046 and did not achieve Worst Pruritus NRS reduction ≥ 4 at Week 24 of Study M16-046.

3.4 Safety Endpoints

[figure not shown]
The safety endpoints are described in Section 3.1.

4.0 Analysis Populations

Significant non-compliance was identified at a site. As a result of this finding, subjects enrolled in this site will not be included in any analysis population and data collected from this site will not be included in any analysis.

The following populations will be used for the analyses.

The Intent-to-Treat (ITT) Population consists of all enrolled subjects who receive at least one dose of study drug in the study and will be used for the efficacy analyses.

The Safety Population is the same as the ITT Population for this study. This population will be used to provide a comprehensive summary of safety.

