7.2 Definition for Analysis Populations

The Intent-to-Treat (ITT) Population consists of all subjects who receive at least one dose of study drug in the study and will be used for the efficacy analyses.

The Safety Population is the same as the ITT Population for this study. This population will be used to provide a comprehensive summary of safety.

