5.0 Subject Disposition

The total number of subjects who were treated will be summarized.

The number of subjects for each of the following categories will be summarized by treatment group randomized in M16-046 in the ITT Population:

- Subjects who completed protocol-specified treatment;
- Subjects who prematurely discontinued study drug (all reasons and primary reason);
- Subjects who completed the study;

Number and percentage of subjects who discontinued study drug will be summarized by reason (primary reason and all reasons). Subjects with multiple reasons for premature discontinuation will be counted once in the calculation of the number and percentage of total discontinuations.

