10.0 Safety Analyses

10.1 General Considerations

Safety data will be summarized for the Safety Population. Safety summaries will include data collected from the first dose of updacitinib in Study M16-046 or Study M19-850, whichever is earlier.

All the safety related endpoints will be summarized for the following three groups, unless otherwise specified:

- Subjects originally randomized to dupilumab in Study M16-046 and continued in Study M19-850
- Subjects originally randomized to upadacitinib in Study M16-046 and continued in Study M19-850
- All the subjects dosed in Study M19-850

For laboratory and vital sign tables, only the first two groups will be included.

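### SAP 4.0 drops one site from every analysis, safety included, without saying whether any count or listing will show that site's treated subjects and serious events

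*SAP*

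**What the plan says.** SAP 4.0 opens with the finding of significant non-compliance at one site and draws two consequences. The first concerns people: "subjects enrolled in this site will not be included in any analysis population". The second concerns their records, in equally general terms: "data collected from this site will not be included in any analysis". It makes no exception for safety. The ITT definition follows directly and "consists of all enrolled subjects who receive at least one dose of study drug in the study"; the Safety Population is the same set. Safety data are summarized for the Safety Population (SAP 10.1).

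Protocol 7.2, in the supplied version, has no site exclusion: "The Intent-to-Treat (ITT) Population consists of all subjects who receive at least one dose of study drug in the study". It also makes the Safety Population the same set.

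The change is declared. SAP 1.0 states "This SAP includes changes to analyses described in the protocol" and points to Section 14.0, where the site exclusion is the only change logged for version 5.0 (01 August 2023). The list in SAP 3.1 that begins "The primary safety endpoints are" covers TEAEs, SAEs, AESIs, AEs leading to discontinuation, and vital signs, laboratory and physical findings. There is no primary efficacy endpoint.

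Two places might account for the excluded site. SAP 5.0 says "The total number of subjects who were treated will be summarized". SAP 10.2.7 plans listings of treatment-emergent SAEs, discontinuation TEAEs, deaths and treatment-emergent AESIs. Neither mentions the site.

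**The concern.** In a single-arm extension whose primary purpose is safety, a reader expects every dosed subject to be accounted for, even when some data are judged too unreliable to summarize. Doubtful records are a reason to keep a site out of rates and means. It does not follow that a death or SAE in a treated subject should be invisible in the study's own outputs.

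As written, the rule could have that result. If the treated total and the listings are produced without the site, nothing in the planned outputs shows how many treated subjects were removed, how much exposure they had, or whether any of them died or had a serious event. What is at stake is rare serious events, where one case decides whether a table shows a signal or a zero. Common event rates are not the issue.

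**Working it through.** **Step 1. Look for a planned output that reaches the excluded site.**

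- SAP 5.0, treated total: names no population, while the disposition rows that follow are tied to the ITT Population. Whether the site is in the total is not stated. If it is in, the number excluded is the treated total minus the ITT number. If it is out, no count exists.
- SAP 6.0, exposure: Safety Population only, so the site's patient-years are out.
- SAP 10.2.2 to 10.2.6, AE tables: Safety Population by way of 10.1, so the site is out. The third reporting group in 10.1, "All the subjects dosed in Study M19-850", is most naturally read as everyone within that reduced population.
- SAP 10.2.7, listings: SAP 4.0 bars the data from any analysis and is silent on listings. Whether the site's events are listed is not stated.
- SAP 10.5, 10.6 and 11.0: no safety subgroup, other safety or other analyses.
- Appendix A: five subject-level deviation categories, not designed to record an excluded site.

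Result: two outputs are unclear, the rest exclude the site, and none is dedicated to it.

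**Step 2. Scale.** The documents do not give the site's size or events, so these are illustrations. Inputs: about 600 subjects (SAP 2.4) and up to 150 sites (protocol synopsis), hence a planned average of 600/150 = 4 per site. A site of 20 is an assumed upper what-if.

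*One rare case, located at the site of 4.* With the site: 1/600 = 0.17%, exact (Clopper-Pearson) 95% CI 0.00-0.93%. Without it: 0/596 = 0%, CI 0-0.62%.

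*Chance that the site holds at least one of k cases, if cases fall evenly* (hypergeometric):
- k = 1: 4/600 = 0.7%; 20/600 = 3.3%.
- k = 3, site of 4: 1 - (596 x 595 x 594)/(600 x 599 x 598) = 2.0%.
- k = 3, site of 20: 1 - (580 x 579 x 578)/(600 x 599 x 598) = 9.7%.

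*Chance that the site has any subject with an event of assumed per-subject risk r*, 1 - (1 - r)^m:
- r = 1%: 3.9% (m = 4), 18.2% (m = 20).
- r = 5%: 18.5% (m = 4), 64.2% (m = 20).

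*Common TEAE at an assumed 60% (360/600):*
- Site of 4, all possible splits: 356/596 = 59.7% to 360/596 = 60.4%.
- Site of 20, central 95% of splits (8 to 16 cases removed): 344/580 = 59.3% to 352/580 = 60.7%.

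*Exposure removed with 4 completing subjects*, 4 x weeks x 7/365.25. Safety exposure starts at the first upadacitinib dose in either study:
- Former dupilumab arm, 52 weeks: 4.0 patient-years.
- Former upadacitinib arm, 24 + 52 = 76 weeks: 5.8.
- Former dupilumab arm in an extended country, 136 weeks: 10.4.
- Former upadacitinib arm in an extended country, 24 + 136 = 160 weeks: 12.3.

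**The case against.** The strongest reply is that excluding data from a site with significant non-compliance is legitimate, and that this exclusion is stated, given a reason and logged. That stands, and nothing here asks for the site to go back into the main tables. The stated reason covers all of the site's data, so a further sentence specific to safety would be welcome but is not required.

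A second reply is that serious events still reach the sponsor: SAEs within 24 hours and SUSAR reporting (protocol 6.1, 6.5), and adjudication of cardiovascular events (6.3). That is correct, but those routes do not put an event into this study's tables or listings.

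A third is that the numerical effect is small. For common events it is, as the figures show.

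Several stronger readings are tempting and are not supported:
- *The plan shows no count and no deaths from the site.* The treated total and the listing of deaths might include it. The text leaves this open.
- *SAP 4.0 contradicts itself.* The exclusion paragraph precedes the definitions and governs them. The unqualified labels in 4.0, 10.1 and the death outputs are matters of editing.
- *The SAP departs from the protocol in force in August 2023.* The supplied protocol has a synopsis dated 07 January 2021 and 52 weeks of treatment, whereas the SAP describes assessments to Week 136 in ten countries and regions. Only a departure from the supplied version can be shown.
- *Interim and final results rest on different subjects.* The rule is dated 875 days after the interim cutoff (09 March 2021 to 01 August 2023), but the documents do not say which subjects the interim tables included. With no statistical testing planned, no error rate is affected.

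**Conclusion.** The concern holds as a gap in accounting for treated subjects. SAP 4.0 takes one site's subjects and data out of every population and analysis, the primary safety endpoints included. The SAP leaves unstated whether the treated total and the AE listings cover the site, and it plans no separate count or listing. A death, SAE, AESI or AE leading to discontinuation in a subject dosed there may appear in no study output.

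The size cannot be settled from the documents. Under the assumed site sizes of 4 and 20, common TEAE rates move by less than one percentage point, and a lone rare case is unlikely to sit at the site (0.7% or 3.3%). If it does, the reported count goes from one to zero and the planned outputs may give the reader no way to know. These figures assume 600 subjects and evenly spread cases, and the patient-year figures assume full completion. The change is worth making because it is cheap and leaves the main analysis untouched. The plan does not show that any event has been lost.

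**What to change.** Keep the exclusion from the main analyses and make two additions:

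1. **SAP 5.0:** report the number of treated subjects and the patient-years of upadacitinib exposure excluded with the site, by M16-046 arm. State whether the treated total includes the site.
2. **SAP 10.2.7:** add a separate listing of deaths, SAEs, AESIs and AEs leading to discontinuation at the excluded site, footnoted for data quality. State that the other listings leave the site out.

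The count would also let a reader reconcile interim and final denominators if they differ.

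Writing the exception into the ITT and Safety definitions, and qualifying the labels for all dosed subjects and all deaths, is editorial. An AE overview repeated with the site included is optional and depends on whether its records can be verified.

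The cost is SAP wording, one count by arm and one listing from data already collected. The downside is that some possibly unverifiable data are shown, which the footnote should say plainly.
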